4.1. Primary Outcome

Incidence of postoperative shoulder pain

4.2. Secondary Outcomes

4.2.1 Quantitative grading of Shoulder Pain using Visual Analog Scale (VAS) for pain score

4.2.2 Cumulative intraoperative insufflation pressure (mmHg min) during the surgery

4.2.3 Subjective grading of quality of surgical exposure expressed by surgeon at end of case using Surgical Rating Scale (Martini, Boon, Bevers, Aarts, & Dahan, 2013)

4.2.4 Readiness to discharge from the Post-Anesthesia Care Unit (PACU) as determined by a modified version of the Dansk Selskab for Anæstesiologi og Intensiv Medicin (DASAIM) discharge criteria scoring system to be completed at 15, 45 and 90 minutes after admission to the PACU

4.2.5 Degree of Post-Operative Nausea and Vomiting (PONV) per Visual Analog Scale and number of episodes of emesis per nurse in PACU

4.2.6 Length of Intensive Care Unit (ICU) & Hospital stay, 30-Day Mortality and Readmission Rate

4.2.7 Measures of organ dysfunction and perfusion by the Postoperative Morbidity Survey (De novo need for oxygen supplementation, ability to tolerate an enteral diet, oliguria or Acute Kidney Injury, Delirium or new neurological deficits) and postoperative lactate

4.3. Exploratory Outcomes

4.3.1. Optional: Incidence of residual muscle relaxation upon admission to PACU as defined by Train-Of-Four (TOF) ratio <0.9, if TOF-Watch[®] SX is available

4.3.2. Optional: Subgroup analysis on elderly patients with comorbidities including laboratory evidence of sarcopenia (creatinine/cystatin c ratio)

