6.1. Intraoperative Anesthesia Care

All patients will receive a balanced general anesthesia with endotracheal intubation and volatile anesthetic agents. In order to avoid excessive sedation in the PACU, no long acting anesthetic agents (ketamine, dexmedetomidine, etc.) or narcotics (hydromorphone, morphine) will be allowed. Short acting narcotics (fentanyl) are allowed.

Patients will be randomized to receive either the Deep Neuromuscular Blockade (DNMB group) with Sugammadex reversal or Moderate Neuromuscular Blockade (MNMB group) with neostigmine reversal. The patients will be started on a continuous Rocuronium intravenous infusion following intubation. Insert recommendations and Institutional Standards will be used for Rocuronium. For the DNMB group, the rate will be adjusted and boluses given to maintain 1-2 post tetanic responses during the pneumoperitoneum. NMB will be reversed with Sugammadex at the end of surgery. For the MNMB group, the Rocuronium infusion rate will be adjusted to maintain 1-2 TOF responses and will be reversed with neostigmine at the end of surgery. The level of NMB will be assessed by the anesthetist with a standard nerve stimulator at 20 minute intervals for both groups.

During the surgical time-out and at the time of insufflation, the surgeon will be instructed to maintain the lowest insufflation pressure necessary for good surgical exposure and safety throughout the operation. All adjustments to the insufflation pressure will be directed by surgeon.

A clinical coordinator will calibrate the acceleromyography (TOF-Watch® SX, Organon Ireland Ltd., a subsidiary of Merck & Co., Inc., Swords, Co. Dublin, Ireland; pending availability due to product discontinuation by manufacturer) at the adductor pollicis muscle during induction prior to neuromuscular blockade, will record insufflation pressure changes during surgery and acquire the TOF ratio (TOFR) with the TOF-Watch® SX upon arrival of each patient to the PACU. Data will be collected from the electronic medical record (Anesthetic Record, PACU notes, Progress notes, Discharge summary, etc.) as well as a PACU survey.

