6.2. Assessment of Outcomes

6.2.1. Depth of Neuromuscular Blockade: When possible, acceleromyography (TOF-Watch® SX, Organon Ireland Ltd., a subsidiary of Merck & Co., Inc., Swords, Co. Dublin, Ireland) at the adductor pollicis brevis muscle will be calibrated during induction but prior to muscle relaxation. The responses from the peripheral nerve stimulator and the site of application used by the anesthetist will be recorded at 20 minute intervals throughout the procedure. A TOF ratio per acceleromyography will be measured upon arrival to the PACU.

6.2.2. Insufflation pressure: Intra-abdominal insufflation time and pressure will be directed by the surgeon and recorded continuously by the clinical coordinator until the time of desufflation.

6.2.3. Surgical Exposure: At the end of the procedure, the surgeon will use the Surgical Rating Scale to describe the quality of surgical exposure. (Martini, Boon, Bevers, Aarts, & Dahan, 2013)

Table 1

The surgical rating score

- 1 *Extremely poor conditions:* the surgeon is unable to work because of coughing or because of the inability to obtain a visible laparoscopic field because of inadequate muscle relaxation. Additional neuromuscular blocking agents must be given
- 2 *Poor conditions:* there is a visible laparoscopic field, but the surgeon is severely hampered by inadequate muscle relaxation with continuous muscle contractions, movements, or

both with the hazard of tissue damage. Additional neuromuscular blocking agents must be given

3 *Acceptable conditions:* there is a wide visible laparoscopic field but muscle contractions, movements, or both occur regularly causing some interference with the surgeon's work. There is the need for additional neuromuscular blocking agents to prevent deterioration

4 *Good conditions:* there is a wide laparoscopic working field with sporadic muscle contractions, movements, or both. There is no immediate need for additional neuromuscular blocking agents unless there is the fear of deterioration

5 *Optimal conditions:* there is a wide visible laparoscopic working field without any movement or contractions. There is no need for additional neuromuscular blocking agents

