8.4. Emergency Actions

Merck, Inc. accepts the right of the Investigator to deviate from the protocol in an emergency and/or break study drug blinding when necessary to safeguard the life or the physical well-being of a study patient. If a patient is displaying signs and/or symptoms of residual neuromuscular blockade that jeopardizes the safety of the patient, the anesthesiologist may decide to administer an additional amount of Sugammadex. In such an event, the patient will remain in the intention to treat group but will be excluded from the analysis between the two treatment groups. The Investigator must give notice of any emergency deviations and justification for the deviation to Merck and the IRB as quickly as possible after the episode, in any event no later than 24 hours after the emergency.

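### Exploratory outcome 4.3.1 does not capture residual blockade treated with additional Sugammadex before the PACU reading, whether the rescued patient is excluded (8.4) or kept

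*Combined protocol and SAP*

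**What the plan says.** - **Outcome.** Section 4.3.1, marked optional and conditional on the TOF-Watch SX being available, is "Incidence of residual muscle relaxation upon admission to PACU as defined by Train-Of-Four (TOF) ratio <0.9". Section 6.2.1 fixes the timing: "A TOF ratio per acceleromyography will be measured upon arrival to the PACU". Section 6.1 has a clinical coordinator take this reading.
- **Assigned reversal.** Under 6.1 the deep-block arm receives Sugammadex at the end of surgery. The moderate-block arm "will be reversed with neostigmine at the end of surgery". Both precede the PACU reading.
- **Rescue.** Section 8.4: "If a patient is displaying signs and/or symptoms of residual neuromuscular blockade that jeopardizes the safety of the patient", then "the anesthesiologist may decide to administer an additional amount of Sugammadex". It names no arm and no time window.
- **Analysis of rescued patients.** Section 8.4 continues: "the patient will remain in the intention to treat group but will be excluded from the analysis between the two treatment groups".
- **Blinding.** Section 4.7 blinds the TOF-watch assessors to the study drug. The anesthesiologist knows the drug but is blinded to the TOF-watch response.
- **Analysis plan.** Section 4.9 names Fisher's exact or chi-square tests for categorical variables. It mentions neither residual blockade nor rescue.

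**The concern.** Rescue under 8.4 is triggered by the very condition that 4.3.1 is meant to count. The interval between end-of-surgery reversal and PACU arrival is within the rescue rule as written, and the anesthesiologist, who does not see the TOF-watch response, has no reason to wait for the reading. A patient rescued in that interval may arrive with an adequate ratio because of the rescue drug. For a patient assigned neostigmine, that drug is the other arm's reversal agent.

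Section 4.3.1 has no rule for this case. The most evident failures of the assigned reversal can therefore go uncounted. The Background describes Sugammadex reversal as more complete, so rescue would be expected mainly in the neostigmine arm and the observed difference would shrink. At stake is the only listed outcome that directly measures residual blockade. The definition of the primary outcome is not affected.

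**Working it through.** **The plan's own figure.** Section 4.8 states 88% power with 48 per group for shoulder pain of 60% v 28.6%, two-sided 0.05. A pooled-variance chi-square calculation without continuity correction gives 88.5%, so it reproduces. This point uses only the 48 per group; the plan gives no figure for 4.3.1.

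**Assumptions (the documents give no residual-blockade or rescue rates).** There are 48 assessed patients per arm. Residual blockade is present before the reading in 12 neostigmine and 2 Sugammadex patients. Of the 12, k = 2, 4 or 6 are rescued before the reading. All rescued patients reach a ratio of 0.9 or more on arrival, and nobody is rescued in the Sugammadex arm.

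**Formulas for the neostigmine arm.**
- Rescue counted as an event: 12/48.
- Excluded, as 8.4 says: (12 − k)/(48 − k).
- Kept, arrival reading only: (12 − k)/48.

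The Sugammadex arm is 2/48 = 4.2% throughout. P-values are two-sided Fisher exact.

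| k | Rule | Neostigmine arm | Difference (points) | p |
|---|---|---|---|---|
| any | rescue is an event | 12/48 = 25.0% | 20.8 | 0.007 |
| 2 | excluded | 10/46 = 21.7% | 17.6 | 0.013 |
| 2 | reading only | 10/48 = 20.8% | 16.7 | 0.027 |
| 4 | excluded | 8/44 = 18.2% | 14.0 | 0.044 |
| 4 | reading only | 8/48 = 16.7% | 12.5 | 0.09 |
| 6 | excluded | 6/42 = 14.3% | 10.1 | 0.14 |
| 6 | reading only | 6/48 = 12.5% | 8.3 | 0.27 |

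**Sensitivity to the assumed counts.** With 10 v 1 true cases and k = 4, the neostigmine incidence is 10/48 = 20.8% with rescue as an event (p = 0.008), 6/44 = 13.6% excluded (p = 0.052) and 6/48 = 12.5% reading only (p = 0.11). The pattern is the same: both rules lose the rescued cases, and exclusion shrinks the difference slightly less.

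**The case against.** **A reader might infer that the plan scores a rescued patient as free of residual blockade.** The documents do not support that. In the between-group comparison 8.4 removes the patient from both numerator and denominator. The patient is a non-event only in a summary that keeps everyone, and only if the arrival ratio is 0.9 or more; a rescued patient could still read below that. For the comparison as written, the exclusion rows of the table apply. This stands, but exclusion loses the same cases in the same direction.

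**The timing and the arm are not stated.** Section 8.4 does not say whether rescue comes before or after the reading, and rescue after it cannot alter the outcome. The reference to an additional amount of Sugammadex also leaves some doubt whether neostigmine patients are meant, although no arm is excluded. Both limits stand: the documents permit the problem but do not show how often it would arise. Six of 12 cases rescued is a high upper end, given the safety threshold for rescue.

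**A ratio of 0.9 or more on arrival is correctly classified under the written definition.** This is true. Blockade present on arrival and failure of the assigned reversal are different quantities. For a trial whose randomized comparison includes the reversal agent, the second is informative, so the plan should say which it intends and how rescue enters.

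**Counting rescue as an event brings in an unblinded decision.** This is the strongest objection to the remedy. The anesthesiologist knows the study drug, whereas the TOF assessor is blinded. It does not remove the gap, but the TOF-only result must stay visible.

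**The outcome matters little.** It is optional and exploratory, has no power calculation, and depends on a device that 6.1 describes as discontinued by its manufacturer. Patient-specific deviations also go on a case report form (8.5), which may allow rescues to be counted by arm. This lowers the priority without supplying a scoring rule.

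**Conclusion.** The point holds in a limited form. Outcome 4.3.1 has no rule for residual blockade treated before the PACU reading, and 8.4 both retains such patients in the intention-to-treat group and drops them from the comparison. Under either handling a rescued case can go uncounted, probably mainly in the neostigmine arm, and a difference would be understated.

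Under the assumed 12 v 2 of 48 with 2 to 6 rescues, 20.8 points become 17.6–10.1 with exclusion or 16.7–8.3 with the reading alone. These sizes rest on assumed rates, on all rescues being in one arm and before the reading, and on every rescued patient reaching 0.9. The direction rests on the Background's view that Sugammadex reversal is more complete. The consequence is confined to an optional exploratory outcome. It is worth correcting because the correction is cheap.

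**What to change.** The change is to analysis and recording only; when and how rescue is given is untouched.

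1. **8.4:** amend the exclusion sentence so that, for 4.3.1, all randomized patients with the outcome assessed stay in the between-group comparison in their assigned arm. Without this, rescoring the outcome has no effect on the comparison.
2. **4.3.1 and 4.9:** count as an event a TOF ratio below 0.9 on PACU arrival, or any Sugammadex given beyond the assigned reversal before that reading.
3. **Sensitivity analysis:** show the TOF-only result, from the blinded assessor, beside the composite, and state that the rescue component is decided by an anesthesiologist not blinded to study drug.
4. **Recording:** note the time of any rescue relative to the reading and report the number rescued by arm.

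The cost is about one sentence in each of the three sections. The anesthetic record is already a data source under 6.1, so little extra collection is expected. The price is an exploratory outcome that becomes a composite with an open-label component, which is why item 3 is needed.

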4.4. Design

Single-center randomized controlled double-blind trial. Patients will be randomized to receive either the Deep Neuromuscular Blockade (DNMB group) or Moderate Neuromuscular Blockade (MNMB group).

4.5. Eligibility

4.5.1. Inclusion Criteria:

- Patients 65 years of age or older
- Patients having robotic prostatectomy
- Written informed consent

4.5.2. Exclusion Criteria:

- Patient with known hypersensitivity to Rocuronium, Sugammadex or its components
- Patients with severe renal insufficiency, defined and confirmed by an estimated creatinine clearance equal or lower than 30 mL/min, per institutional laboratory.
- Patients with history of severe liver disease, defined as and confirmed by elevated ALT and AST greater than 1.5 times the Upper Limit of Normal along with Albumin less than 3 **OR** INR 1.5 or greater per institutional laboratory.

Patients will be identified when scheduled for Robotic Prostatectomy. Eligible subjects will be approached before scheduled surgery to obtain Informed Consent. Consent will be obtained by Investigator, Co-Investigator and/or Collaborators; the process will be documented in EPIC.

After Informed Consent is obtained, we will collect Demographics, Laboratory Test results of interest for the study, Concomitant Medications taken within 30 days prior surgery and Neoadjuvant Chemotherapy if any.

4.6. Randomization

Once it has been determined that the patient meets all eligibility criteria, they will be randomized on a 1:1 ratio for Deep Neuromuscular Blockade and Sugammadex or Moderate Neuromuscular Blockade and neostigmine administration. Randomization will be done the morning of surgery by using REDCap randomization tool.

4.7. Blinding, Allocation and Concealment

Patients and TOF-watch assessors will be blinded to the study drug. The assessor of the primary outcome will not be involved in randomization, or allowed in the operating room during surgery. Anesthesiologists will not be blinded to study drug but he/she will be blinded to the TOF watch response. The surgeon and PACU staff will be blinded to the group assignment.

4.8. Sample Size Justifications

For 99 patients undergoing laparoscopic hysterectomy, 28.6% of the DNMB group (IP 8mmHg) vs. 60% in the MNMB group (IP 12mmHg) experienced shoulder pain. (Madsen, et al., 2016)

Using the data from the aforementioned study, a sample size of 48 per group will enable the study 88% power to detect the decrease in the rate of postoperative shoulder pain from 60% for the control group to 28.6% for the group with deep Neuromuscular Blockade and Sugammadex, assuming a two-sided type I error rate of 0.05 using a two-group Chi-square test (nQuery Advisor 7.0). Postoperative shoulder pain is defined as any shoulder pain recorded before the discharge from PACU. We predict that the typically increased length of robotic surgery in combination with potentially lower insufflation pressures (6-7mmHg) may result in an even greater difference between the two groups. We want to factor in a 4% drop-out rate, therefore, we will enroll a total of 100 patients.

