One possible subgroup that may receive the greatest benefit from the use of Sugammadex are cancer patients with sarcopenia and sarcopenic obesity. Cancer cachexia affects 60-80% of patients with advanced cancer and is associated with increased morbidity and mortality. (Baracos, 2011) Though criteria for cancer cachexia has traditionally varied, an international panel of cachexia experts recently agreed upon a common definition which includes recent weight loss, BMI and sarcopenia. Among 1,077 cancer patients, those classified as cachectic, as defined by weight loss greater than 5% over the last 6 months or greater than 2% with a BMI less than 20 kg/m², had a shorter median survival than for non-cachectic patients. (139 versus 269 days; $P < 0.001$) (Blum, 2014) Among cancer patients to receive chemotherapy, those with sarcopenia had a mortality hazard ratio of 5.19 when controlled for BMI, age and tumor stage. (Gonzalez, 2014)

A laboratory indicator of sarcopenia is the creatinine to cystatin c ratio, which can account for the majority of individual variability of total body muscle mass and has been used to detect sarcopenia and sarcopenic obesity. (Kim, et al., 2016) Cystatin C also has greater prognostic value than creatinine. (K Suzuki, 2015) (Y Otaki, 2015) (Graf, 2015) (Wannamethee, 2015)

The Postoperative Morbidity survey is a 9-point scale used to systematically assess short-term morbidity and multi-organ dysfunction following surgery. (Bennett-Guerrero, et al., 1999) (Davies, et al., 2013) It has been shown to have good reliability and validity with an association with greater hospital length of stay in the general population and increased mortality in the elderly. (Howes, et al., 2015)

2. Hypotheses

2.1 Elderly patients undergoing robotic prostatectomy who receive continuous deep neuromuscular blockade and its reversal with Sugammadex will have adequate surgical exposure with lower insufflation pressures which will be associated with lower postoperative shoulder pain, less morbidity and a faster recovery when compared to patients receiving moderate neuromuscular blockade.

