4.9. Analysis Plans

Patients' demographic information, laboratory test results and concomitant medications, including neoadjuvant chemotherapy at baseline will be analyzed, with data summarized in tables listing the distributions of the variables along with the number of subjects per treatment arm in order to assess comparability. Patients' information on post-operative shoulder pain, nausea, vomiting, intubation and measures from Postoperative Morbidity Survey will be collected. The Fisher's exact test or Chi-square test will be applied to assess the association between two categorical variables. We will summarize the distribution of average and cumulative intraoperative insufflation pressure, Post Anesthesia discharge DASAIM scores, length of ICU and hospital stay by each treatment. We will use the student t-test or the Wilcoxon rank sum test to compare continuous variables between two different patient groups. Logistic regression will be utilized to assess the effects of patient prognostic factors, comorbidities and treatment on postoperative shoulder pain and postoperative morbidity.

Adverse event (AE) data will be summarized by frequency tables. The association between the types and severity of AE and the treatment will be evaluated.

5. Study Drug Information

Since both Sugammadex and Neostigmine are FDA approved, Insert recommendations and Institutional Standards will be followed for all study agents.

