6.2.4. Postoperative Pain: A Survey will be completed by the PACU nurse. The patient will be asked if INCISIONAL, VISCERAL and/or SHOULDER PAIN are present. The nurse will record Visual Analog Scale (VAS) pain score (1-10) for pain in general and for Shoulder Pain if present, recording these separately. All these will be recorded at 15, 45 and 90 minutes (if patient not previously discharged). Opioids administered by the PACU nurse will be measured in morphine equivalents.

6.2.5. Readiness to Discharge from PACU: Readiness to discharge from the PACU as determined by a modified version of the DASAIM discharge criteria scoring system (Gartner, Callesen, Kroman, & Kehlet, 2010) (Phillips, Street, Kent, Haesler, & Cadeddu, 2013) to be completed at 15, 45 and 90 minutes (if patient not previously discharged) after admission to the PACU. A patient will be considered ready for discharge if cumulative score is 4 or less and no single category has a score greater than 1.

DASAIM Discharge Criteria Scoring System (Gartner, Callesen, Kroman, & Kehlet, 2010)		
Sedation	0	Patient is fully awake
(Nurse Evaluation)	1	Patient is asleep, aroused by verbal stimulation
	2	Patient is asleep, aroused by physical stimulation
	3	Patient is asleep, cannot be aroused
Respiratory Rate	0	Respiratory rate > 10
(Nurse count)	1	Snoring, 10 < RR <30
	2	RR < 10 or RR > 30/min
	3	Periods of apnea or obstructive patterns
Oxygen Saturation	0	SpO2 ≥ 94%
(No supplemental oxygen for 10 minutes)	1	90% ≤ SpO2 < 94%
	2	85% ≤ SpO2 < 90%
	3	SpO2 < 85%

Systolic Blood Pressure	0	SBP \geq 100mmHg
	1	90mmHg \leq SBP < 100mmHg
	2	80mmHg \leq SBP < 90mmHg or SBP > 220mmHg
	3	SBP < 80mmHg
Heart Rate	0	50 < HR \leq 100
	1	100 < HR \leq 120
	2	40 < HR \leq 50 or 120 < HR \leq 130
	3	HR < 40 or HR > 130
Pain at rest	0	No pain
(Patient evaluation)	1	Light pain
	2	Moderate pain
	3	Severe pain
Nausea	0	No nausea or vomiting
	1	Light nausea or vomiting without previous nausea
	2	Moderate nausea and/or vomiting
	3	Severe nausea and/or vomiting

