6.2.6. Postoperative Morbidity: Cystatin C will be drawn during pre-procedure and sent to external laboratory for analysis and calculation of the Cystatin C/Creatinine Ratio, to determine if the patient shows laboratory evidence of Sarcopenia. Postoperative lactate level will be drawn in the PACU as well as an arterial blood gas when an arterial line catheter is present. Overall postoperative morbidity will be recorded on POD 1, 3, 5 and 7 using the Postoperative Morbidity Survey assessed by chart review.

Morbidity type	Criteria
Pulmonary	De novo requirement for supplemental oxygen or other respiratory support (e.g., mechanical ventilation or CPAP)
Infectious	Currently on antibiotics or temperature $>38^{\circ}\text{C}$ in the last 24 h
Renal	Presence of oliguria ($<500\text{ mL/d}$), increased serum creatinine ($>30\%$ from preoperatively), or urinary catheter in place for a nonsurgical reason
Gastrointestinal	Unable to tolerate an enteral diet (either by mouth or via a feeding tube) for any reason, including nausea, vomiting, and abdominal distention
Cardiovascular	Diagnostic tests or therapy within the last 24 h for any of the following: de novo myocardial infarction or ischemia, hypotension (requiring pharmacological therapy or fluid therapy $>200\text{ mL/h}$), atrial or ventricular arrhythmias, or cardiogenic pulmonary edema
Neurological	Presence of a de novo focal deficit, coma, or confusion/delirium
Wound complication	Wound dehiscence requiring surgical exploration or drainage of pus from the operation wound with or without isolation of organisms
Hematological	Requirement for any of the following within the last 24 h: packed erythrocytes, platelets, fresh-frozen plasma, or cryoprecipitate
Pain	Surgical wound pain significant enough to require parenteral opioids or regional analgesia

CPAP = continuous positive airway pressure.

(Bennett-Guerrero, et al., 1999)

6.2.7. 30-Day Mortality and Readmission Rate: Patients will be contacted via phone 30 days after being discharged from the Hospital to collect mortality and readmission data. If research staff is not able to contact the patient, this data will be obtained from available medical records.

7. Adverse Events

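### The primary endpoint cannot separate shoulder pain that predates surgery, and its observation time ends at PACU discharge; a baseline question, a stratified analysis and a 45-minute check would cover both

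*Combined protocol and SAP*

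**What the plan says.** The definition of the primary event is in section 4.8: "Postoperative shoulder pain is defined as any shoulder pain recorded before the discharge from PACU". It has no fixed time and no condition that the pain be new.

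Section 6.2.4 describes the nurse survey: "The patient will be asked if INCISIONAL, VISCERAL and/or SHOULDER PAIN are present". On timing it says "All these will be recorded at 15, 45 and 90 minutes (if patient not previously discharged". Section 6.1 adds that study data also come from the electronic record, including PACU notes.

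For baseline, section 4.5 says "we will collect Demographics, Laboratory Test results of interest for the study, Concomitant Medications taken within 30 days prior surgery", together with any neoadjuvant chemotherapy. The exclusions cover hypersensitivity, renal insufficiency and liver disease. Shoulder pain appears in neither list. On allocation, section 4.6 says "Randomization will be done the morning of surgery by using REDCap randomization tool".

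In section 4.9, Fisher's exact test is the alternative to the test in this sentence: "Chi-square test will be applied to assess the association between two categorical variables". A logistic regression of shoulder pain on prognostic factors, comorbidities and treatment is also planned. Neither baseline shoulder pain nor PACU time is named, and no analysis at a common time is specified.

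Hypothesis 2.1 expects, with deep blockade, "less morbidity and a faster recovery when compared to patients receiving moderate neuromuscular blockade".

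**The concern.** Two features of the endpoint deserve attention.

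**Pain that predates surgery.** The background section attributes the pain of interest to diaphragmatic irritation by carbon dioxide. A shoulder that already hurt before surgery is a different matter, but it scores as an event if the patient mentions it in PACU. Events of this kind, equally common in both arms, pull the two rates together and cost power. Whether a patient had such pain cannot be established reliably once surgery is over.

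**Observation time.** A patient who leaves PACU before 90 minutes has less time in which pain can be recorded. If deep blockade speeds recovery, as hypothesis 2.1 expects, the arms could be observed for different lengths of time. No later structured assessment fills the gap. The pain item in the Postoperative Morbidity Survey is "Surgical wound pain significant enough to require parenteral opioids or regional analgesia", and section 7.5 does not count shoulder pain without ECG changes as an adverse event. The separate 15- and 45-minute records would allow a comparison at a common time, but one chosen after the results are seen would be less credible.

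**Working it through.** **Inputs from the documents (4.8):** 60% v 28.6%, 48 per arm, two-sided 0.05, chi-square test, stated power 88%.

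**The plan's figure.** The mean rate is (0.60 + 0.286)/2 = 0.443.
- Null SE = √(2 × 0.443 × 0.557/48) = 0.1014.
- Alternative SE = √((0.60 × 0.40 + 0.286 × 0.714)/48) = 0.0962.
- Power = Φ((0.314 − 1.96 × 0.1014)/0.0962) = Φ(1.198) = 88.5%.

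Exact binomial enumeration of the uncorrected chi-square test gives 88.6%. The stated 88% is reproduced, and 88.6% is the reference below.

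**Part 1: pain that predates surgery.** Assumptions: a share b of patients in each arm has it; a fraction r of them report shoulder pain in PACU because of it; everyone else follows the arm's rate p; and the cited rates exclude it. The observed rate is p + r·b·(1 − p), so the difference is 0.314 × (1 − r·b). Example with b = 10%, r = 1: 0.60 + 0.10 × 0.40 = 64.0% v 0.286 + 0.10 × 0.714 = 35.7%, a difference of 28.3 points.

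Power at 48 per arm (exact enumeration, except that the stratified rows are simulated with the Cochran-Mantel-Haenszel test):

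| Case | b = 5% | 10% | 15% | 20% |
|---|---|---|---|---|
| As written, r = 1: difference, points | 29.8 | 28.3 | 26.7 | 25.1 |
| As written, r = 1: power | 84.9% | 80.7% | 76.0% | 70.9% |
| As written, r = 0.5: power | 86.8% | 84.9% | 82.9% | 80.7% |
| Stratified, all patients, r = 1 | 86–87% | 85% | 82% | 80% |
| Stratified, all patients, r = 0.5 | 87% | 86% | 84% | 82% |
| Baseline-pain patients left out (45/43/40/38 per arm) | 85.5% | 84.9% | 83.3% | 80.1% |

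If baseline pain is unrelated to PACU reporting (r = 0), the plan as written keeps 88.6% and the stratified test has about 88%. If the cited rates already include such pain, the plan as written also keeps 88.6%.

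**Part 2: observation time.** Assumptions: no true effect; 60% by 90 minutes in both arms; nobody leaves before 45 minutes; departure is unrelated to pain. F45 and F90 are the shares with pain first recorded by 45 and 90 minutes, and d is the share leaving between those times. The observed rate is d·F45 + (1 − d)·F90. Example for the last row: 0.10 × 0.40 + 0.90 × 0.60 = 58.0% v 0.40 × 0.40 + 0.60 × 0.60 = 52.0%, a gap of 6.0 points.

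| F45 (F90 = 60%) | d, moderate v deep | Gap, points | Null rejection | Null rejection, by-45 test |
|---|---|---|---|---|
| 55% | 10% v 20% | 0.5 | 5.0% | 5.1% |
| 52% | 10% v 40% | 2.4 | 5.6% | 5.2% |
| 40% | 10% v 40% | 6.0 | 9.2% | 4.9% |

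Equal departure gives no gap.

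The by-45 test stays near 5% but uses fewer events. With the cited rates at 90 minutes and the same onset pattern in both arms, it compares 0.60·f with 0.286·f, where f = F45/F90 = 0.917, 0.867 and 0.667. Its power is about 83%, 79% and 63%.

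**The case against.** The case on the other side is substantial, and much of it stands.

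- **Unequal observation is hypothetical.** The documents give no PACU-stay figures. The discharge-readiness score is defined, but nothing says what governs actual departure. The 9.2% needs a third of all events to be first recorded after 45 minutes and 40% v 10% early departure, and nothing in the plan supports either figure. A reader might infer that the endpoint is biased towards deep blockade; the documents show only that it could be, if PACU stay differs. This stands.
- **The endpoint is not limited to three survey questions.** PACU notes also feed the data, and section 4.7 blinds patients and PACU staff, which limits differential recording. Both points stand, but the notes end at discharge too, and blinding does not equalise length of stay.
- **Pain until PACU discharge is a legitimate, clearly stated endpoint.** Agreed. The common-time analysis is an addition to it.
- **Pre-existing pain is balanced by randomisation.** Agreed. A reader might infer that it can create a false difference; under 1:1 allocation it does not do so systematically. The loss is in power, and it depends on an assumed prevalence and on how often such pain is reported in PACU.
- **Restricting the primary analysis to patients without baseline pain is not clearly better.** This stands. It gains power over the plan as written when every such patient reports the pain in PACU. At half reporting it is about level (85.5/84.9/83.3/80.1% v 86.8/84.9/82.9/80.7%). If baseline pain is irrelevant, it only loses.

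**Conclusion.** The gap is real and modest. As written, the plan cannot tell prior shoulder pain from new pain, and it pre-specifies no check on unequal observation time.

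The cost of prior pain is lost power: from 88.6% to between 84.9% and 70.9% for prevalences of 5% to 20% with full reporting, to between 86.8% and 80.7% with half reporting, and none if the cited rates already include it or it is unrelated to PACU reporting. The documents do not say whether the cited 60% and 28.6% include it. Prevalence and reporting are assumptions throughout.

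The cost of unequal observation is small in the moderate patterns (5.0% and 5.6% against a nominal 5%) and becomes material only in the extreme one (9.2%). The direction favours whichever arm leaves earlier, and the documents do not establish which arm that is.

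The documents do not support two stronger conclusions: that the primary comparison is already biased, or that the primary population should be cut to patients free of baseline pain. Stratifying all randomised patients has at least the power of the unstratified test under full and half reporting, and comes within about 1 point of it if baseline pain is irrelevant.

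**What to change.** - **Sections 4.5 and 6.2.4:** add one yes/no question on current shoulder pain, asked before randomisation.
- **Section 4.9, primary analysis:** keep all randomised patients and stratify the treatment comparison by the answer. Use a Cochran-Mantel-Haenszel test, or name the answer as a covariate in the logistic regression already planned.
- **Section 4.9, sensitivity analyses:** (a) new-onset shoulder pain among patients who answered no; (b) shoulder pain recorded by 45 minutes, and by 15 minutes if some patients leave before 45. Report the number of assessments completed per arm.
- **Section 4.8:** state whether the cited rates are taken to include pain that predates surgery.

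The cost is one baseline question, a little more analysis and the wording. No new data after surgery are needed, and the sample size stays at 100. The 45-minute comparison has less power (about 83%, 79% and 63% in the patterns above), so it should be labelled supportive and should not replace the primary analysis.
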